Title	Randomized Control Trial Comparing Walking Task Specific Training with Stride Management Assist (SMA) Device vs. Functional Task Specific training on Functional Walking Ability in Outpatient Stroke Rehabilitation.
Short Title	Impairment vs. Functional Walking Training in Sub-Acute and Chronic Stroke (match this to title used it ClinicalTrials.gov)
Protocol Number	STU00085161
Methodology	Randomized Controlled Trial with 2 arms
Study Duration	1 year
Study Center(s)	Single site, multiple clinics within RIC's flagship hospital and it's outpatient clinics
Objectives	Determine if Honda Stride Management Assist vs. traditional Functional Gait Therapy increases Gait speed and function post stroke
Number of Subjects	80
Diagnosis and Main Inclusion Criteria	Cerebrovascular accident (CVA), post 30 days, Gait speed between 0.4 m/s and 0.8 m/s, MMSE > 17, unsupported sitting >30 s, walk at least 10m with up to max assist, follow instructions, physician clearance for participation
Study Product(s), Dose, Route, Regimen	Honda Stride Management Assist device in outpatient physical therapy
Duration of administration	18 Sessions of Outpatient Physical Therapy + 4 Sessions of testing
Reference therapy	Traditional Functional Mobility Training Physical Therapy
Statistical Methodology	Multiple ANOVAs

1.0 BACKGROUND AND RATIONALE

1.1 Disease Background

Stroke is the leading cause of adult-onset of disability. Recent studies estimate that stroke affects about 795,000 people in the U.S. each year, resulting in a prevalence of over 6.4 million individuals^{1,2}. A large proportion of these stroke survivors (up to 80%) experience considerable gait deficits, including reduced walking speeds and asymmetrical walking patterns, limiting their capacity for community ambulation³. These mobility deficits are due to a combination of numerous neuromuscular changes following the stroke including: reduced corticospinal drive and control, muscle atrophy and weakness, impaired balance and posture control, abnormal muscle synergies, and visuo-cognitive deficits.

The goal of post-stroke rehabilitation is to reintegrate individuals back to their highest level of function for employment, social and community participation⁴. The return of mobility and walking is a crucial part of this return to function⁵. Gait training has been a major focus of stroke rehabilitation⁴, with self-selected walking speed considered to be one of the most important measures of stroke rehabilitation. It is thought to be a predictor of health status, community mobility, social interaction, and overall quality of life. Stroke survivors are currently classified based on their self-selected walking speeds as: non-ambulators (unable to walk), limited household ambulators (<0.4m/s), limited community ambulators (0.4-0.8m/s), and community ambulators (>0.8m/s)⁶. These walking speeds are however significantly lower than those exhibited by healthy controls (1.3-1.5 m/s)⁷.

Physical rehabilitation has many methodological approaches to training post stroke. The 2 most commonly applied techniques are task specific training, in this case gait training and impairment based training, which is more focused on balance, and functional deficits. The use of unconstrained robotic exoskeletons may allow gait retraining to be integrated with activities of daily living. However, there are very few studies that looked at the impact of a robotic exoskeleton on walking performance in the mild-moderate-stroke population^{8,9}. This study will compare task specific training using a robotic exoskeleton SMA vs. IPT impairment based physical therapy in the outpatient setting for individuals post-stroke.

1.2 Study Agent(s)/Devices Background

The Stride Management Assist (SMA) System is a robotic device developed by Honda R&D Corporation ®, Japan (<http://corporate.honda.com/innovation/walk-assist/>).

This robotic device assists hip flexion and extension, for each side independently. It is controlled through software run on a tablet. The device weighs 2.8 kgs, and has 2 brushless DC motors running on a rechargeable lithium ion battery. It comes in 3 sizes (small, medium and large). It is worn around like a belt with the motors near the hips and straps on the thighs. The SMA device allows users to increase their stride length by providing assist with the motors in flexion and extension. This device is 1) simple to use in the clinical setting; 2) easily adjustable to alter according to the requirements of each subject; and, 3) can quantify the amount of assistance required to facilitate walking patterns.

1.3 Rationale

There is substantial evidence that post stroke recovery can last for greater than a year³. Due to cost pressures, various forms of therapies have been assessed for their effectiveness and efficiency. Task specific training post stroke has been found to be a very effective strategy for gait retraining^{10,11}. Impairment based physical therapy is another methodology practiced in clinical settings where the training is based on progressive strength and balance exercise program in the outpatient setting¹². The SMA group (task specific training) will be trained to simulate the demands of overground walking. The impairment based group will match the SMA group in intensity but will be focused on balance and other functional goals rather than explicitly on walking. The rationale of this study is to assess task specific training with SMA vs. impairment based training. To this end, we will use the Stride Management Assist device by Honda Corporation and compare it to impairment based physical therapy in outpatient sessions.

The enhancement of corticospinal excitability may help account for the long-term plasticity and improved motor control in people with stroke. To study this, we will measure corticospinal excitability of the lower limb muscles using Transcranial Magnetic Stimulation TMS. TMS is a safe and non-invasive method that has been widely used to study cognition, brain-behavior relations and the pathophysiology of various neurologic and psychiatric disorders.

2.0 STUDY OBJECTIVES

2.1 Primary Objectives

- 2.1.1 To determine the effect on gait speed, as assessed by the 10 meter walk test of the SMA device vs. traditional physical therapy care in an outpatient setting for post stroke individuals.

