2.2 Secondary Objectives

- 2.2.1** To determine the effect on functional walking endurance as assessed by the 6 minute walk test, of task specific training with the SMA device vs impairment based physical therapy in an outpatient setting for post stroke individuals.
- 2.2.2** To determine the effect on functional balance, as assessed by the Berg Balance Scale, Functional Gait Assessment and Five times sit to stand measure as assessed by the 6 minute walk test, of task specific training with the SMA device vs. impairment based physical therapy in an outpatient setting for post stroke individuals.
- 2.2.3** To determine the effect on stroke recovery, as assessed by the step counter of task specific training with the SMA device vs. impairment based physical therapy in an outpatient setting for post stroke individuals.
- 2.2.4** To determine the effect on descending corticospinal drive to the lower limb muscles in training with the Stride Management Assist (SMA) device vs. impairment based physical therapy in an outpatient setting for post stroke individuals.

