4.0 TREATMENT PLAN

4.1 Treatment Sessions

Once subjects have been consented and they meet study inclusion and exclusion criteria, they will be randomly placed into either the SMA group or impairment based (IPT) group. The Physical therapy treatment sessions will follow the guidelines below:

- IPT group
 - Assessment (strength, flexibility, balance, sensation, endurance, transfers, gait). Treatment will be divided into: 15 min balance training, 15 minutes functional mobility (transfers, strength or flexibility training) and 15 min high intensity gait training

- SMA group
 - Assessment (strength, flexibility, balance, sensation, endurance, transfers, gait)
 - Treatment consists of 30minutes high intensity gait training with device, 15 minutes functional mobility with device (eg stairs, ramps, curbs, uneven surfaces, indoors, outdoors)

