
Sitting balance
 
 • Reaching • Perturbations 
Progress to standing
 
Change stance:
 
 • Static • Dynamic • Double limb stance • Romberg • Tandem • Semi-tandem • Unilateral Single limb stance 
Change surface:
 
 • Balance board • Foam cushions, half foam roll • Bosu ball • Balance beam • With/without AFO 
Dual Tasking:
 
 • Ball catch • Cognitive tasks • Reading, visual attention • Perturbations 	
Change surface/stance:
 
 • Level surfaces • Over obstacles • Over compliant surfaces • Tandem walk (forwards/backwards) • With/without AFO 
Multidirectional walking:
 
 • Backwards • Sidestepping • Tandem 
Dual tasking:
 
 • Ball catch • Ball bounce • Cognitive tasks 
Other:
 
 • Increased speed • Pivot turn • Balance beam • Perturbations • Increase distance • Assistive device progression • Reduction in physical assist progression 	
 • Sit to stand transition • Functional up right postures • Reaching • Step up and step down • Stairs • Ramps, curbs • Weights/Theraband • Stretches 
To customize the program, the therapist may adjust the time between the Balance, Dynamic Gait & Functional Mobility needs of the patient.

For the SMA group:

Dynamic Functional Gait – SMA OG 45 min	ALL training for both groups will be High Intensity Training	Home Exercise Program

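### Primary objective 2.1.1 asks a device question, but the arms differ in both device and supervised gait practice, so the design supports only the package contrast already stated in 1.3, 2.2 and 8.1

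*Combined protocol and SAP*

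**What the plan says.** Objective 2.1.1, the only primary objective, concerns the effect on 10-metre walk speed "of the SMA device vs. traditional physical therapy care". The synopsis objective reads "Determine if Honda Stride Management Assist vs. traditional Functional Gait Therapy increases Gait speed and function post stroke". Both name the device as the thing under test, and the synopsis row describes the comparator as a gait therapy.

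Other parts of the protocol ask a different question. Secondary objective 2.2.1 concerns the effect "of task specific training with the SMA device vs impairment based physical therapy", and 2.2.2 and 2.2.3 follow the same pattern. Section 1.3 (Rationale) and section 8.1 also set SMA-based task-specific training against impairment-based therapy. Section 1.3 says that the arms are matched on intensity and that IPT is not aimed explicitly at walking.

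The synopsis gives the design as "Randomized Controlled Trial with 2 arms". Section 4.1 sets the session content:

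- SMA: "Treatment consists of 30minutes high intensity gait training with device, 15 minutes functional mobility with device".
- IPT: "15 min balance training, 15 minutes functional mobility (transfers, strength or flexibility training) and 15 min high intensity gait training".

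The tables in 5.2 keep the three 15-minute blocks for IPT but show SMA as a single 45-minute block of dynamic functional gait. For IPT they add that "the therapist may adjust the time between the Balance, Dynamic Gait & Functional Mobility needs of the patient". Both arms share a home exercise programme based on high-intensity gait training. Section 8.3 plans no summary of the gait time delivered.

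**The concern.** The primary objective governs the headline claim. As 2.1.1 is worded, a faster walking speed in the SMA arm would be reported as a benefit of the device. That arm also receives more supervised walking, and no arm receives the same walking without the device. The rival explanation comes from the protocol itself: section 1.3 calls task-specific training very effective for gait retraining. A device-specific conclusion would therefore be confounded with gait practice, although the randomization is valid.

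The comparator's name adds to the problem. It is traditional physical therapy in 2.1.1, functional gait therapy in the synopsis objective, functional mobility training in the synopsis reference-therapy row, functional task-specific training in the title, and impairment-based therapy in 1.3, 2.2, 4.1 and 8.1. A reader of the synopsis objective alone would assume that both arms received gait therapy and only one had the device.

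**Working it through.** **Inputs**

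- Sessions: up to 18 (4.2).
- IPT, minutes per session: balance 15, functional mobility 15, gait 15 (4.1; same in the 5.2 table).
- SMA, minutes per session: gait 30, functional mobility 15 (4.1); or one 45-minute block (5.2), which includes stairs, ramps and curbs.

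**Step 1. Total scheduled time.** IPT: 15 + 15 + 15 = 45. SMA: 30 + 15 = 45. Contact time is equal; the content differs. In effect, IPT's 15 minutes of balance is replaced by 15 more minutes of gait.

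**Step 2. Gait blocks only (4.1).**

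- SMA: 30 × 18 = 540 min. IPT: 15 × 18 = 270 min.
- Ratio: 540 / 270 = 2.0. Excess: 540 − 270 = 270 min = 4.5 h.

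**Step 3. Functional mobility counted as gait in both arms.** The 5.2 table lists stairs, ramps and curbs in IPT's functional mobility block as well, so the same rule must apply to both arms.

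- SMA: 45 × 18 = 810 min. IPT: (15 + 15) × 18 = 540 min.
- Ratio: 810 / 540 = 1.5. Excess: 810 − 540 = 270 min = 4.5 h.

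The excess is the same in both counts because each reflects the balance block that only IPT has.

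**Step 4. Adding the shared home programme.** The 5.2 table gives a target at discharge of 45 minutes once a day. Time actually done at home is unknown. Assume 6 weeks (18 sessions at 3 per week).

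- Target met every day: 45 × 42 = 1,890 min per arm. Ratios: (540 + 1,890) / (270 + 1,890) = 2,430 / 2,160 = 1.13; (810 + 1,890) / (540 + 1,890) = 2,700 / 2,430 = 1.11.
- Half of that (945 min): 1,485 / 1,215 = 1.22; 1,755 / 1,485 = 1.18.

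The first case is an upper bound on dilution, since the target is to be worked up to by discharge. The 270-minute supervised excess remains.

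**Step 5. Can the two components be separated?** Write the arm difference as D + G. D is the effect of wearing the device given the SMA session content, and G is the effect of that content instead of IPT content, without the device. Two arms estimate the sum only: one contrast, two unknowns. No analysis of these two arms identifies D without an outside assumption about G.

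**Step 6. What separating them would take.** It needs an arm with matched gait time and no device. At 40 per arm that is 3 × 40 = 120 participants. Within 80 it is 80 / 3 ≈ 26.7 per arm, or about 26.7 × 0.7 ≈ 18.7 completers at the stated 30% attrition. The two-arm plan has 40 × 0.7 = 28. The detectable standardized difference is (1.645 + 0.842) × √(2/n), with alpha 0.10 from 8.3 taken as two-sided and 80% power assumed. It is 0.66 SD at n = 28 and 0.83 SD at n = 18.

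**The case against.** The strongest reply is that the package contrast is deliberate and declared. The title, 1.3, 2.2.1–2.2.3 and 8.1 all set walking training with the SMA against a different style of therapy, so unequal gait practice is the intended contrast. Objective 2.1.1 can be read as shorthand, and nothing in section 8 plans a claim that isolates the device. This stands, and it limits the point to a mismatch between the primary objective and the design. It does not remove the mismatch, because 2.1.1 and the synopsis objective are the statements from which the main result will be reported.

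Three qualifications also stand. The home programme is gait-based in both arms and dilutes the difference in total practice. IPT minutes are nominal because the therapist may reallocate them. The 4.1 and 5.2 descriptions of the SMA session both total 45 minutes, so they may be one session labelled in two ways and need not be two competing gait doses.

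A reader might set the 45-minute SMA block against IPT's 15-minute gait block and infer a three-fold difference. The documents do not support that: it counts stairs, ramps and curbs as gait in one arm and not in the other.

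**Conclusion.** The point holds as a mismatch between the primary objective and the design. As written, 2.1.1 and the synopsis objective invite a device-specific conclusion. The two arms support only a conclusion about task-specific gait training with the SMA versus impairment-based therapy. The nominal supervised gait difference is 1.5- to 2-fold, 270 minutes (4.5 hours) over 18 sessions. This assumes that all 18 sessions are attended and the scheduled blocks are delivered as listed. The confounding does not depend on the exact ratio.

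Two stronger readings are not supported. The first is that extra practice would produce a gain of a particular size in m/s: the documents give no rate linking gait minutes to speed, so no such figure can be derived. The second is that a null result would be uninterpretable. For the package question, therapist tailoring is part of the comparator, and a null result can still be read as a comparison of two strategies. Nor is the choice of a package comparison itself an error.

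**What to change.** 1. Reword 2.1.1 and the synopsis objective to the comparison made: the effect on 10-metre walk speed of task-specific gait training with the SMA device versus impairment-based physical therapy.
2. Use one name for the comparator throughout, including the title and both synopsis rows.
3. State in 8.3 that a difference between arms will be interpreted as an effect of the package and not of the device alone.
4. Record gait minutes delivered at each session in both arms and report them descriptively by arm. The session record named in 5.2 is the hospital's clinical system, and the documents do not show whether a field can be added to it; the case report form is the alternative.
5. Reconcile the 4.1 and 5.2 descriptions of the SMA session.

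The cost is protocol wording, one recorded field and a narrower claim for the device. The sample size stays at 80, with no added visits or arms. If a device-specific claim is essential to the sponsor, rewording will not provide it; a gait-matched arm without the device would be needed, at the cost shown in the working.

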2.2 Secondary Objectives

- 2.2.1** To determine the effect on functional walking endurance as assessed by the 6 minute walk test, of task specific training with the SMA device vs impairment based physical therapy in an outpatient setting for post stroke individuals.
- 2.2.2** To determine the effect on functional balance, as assessed by the Berg Balance Scale, Functional Gait Assessment and Five times sit to stand measure as assessed by the 6 minute walk test, of task specific training with the SMA device vs. impairment based physical therapy in an outpatient setting for post stroke individuals.
- 2.2.3** To determine the effect on stroke recovery, as assessed by the step counter of task specific training with the SMA device vs. impairment based physical therapy in an outpatient setting for post stroke individuals.
- 2.2.4** To determine the effect on descending corticospinal drive to the lower limb muscles in training with the Stride Management Assist (SMA) device vs. impairment based physical therapy in an outpatient setting for post stroke individuals.

2.3 Endpoints

The outcome measures will be assessed prior to the start of Outpatient Therapy, after 9 Outpatient PT visits , after 18 sessions and a 3 month follow up testing visit, which will be the endpoints of the study;

3.0 PATIENT ELIGIBILITY

Potential subjects will be recruited from RIC's scheduling for outpatient physical therapy. They will be consented and must fulfill the following criteria:

3.1 Inclusion Criteria

- \geq 30-days post stroke
- Age: 18-85 Years
- Initial gait speed of > 0.4 m/s and < 0.8 m/s
- Adequate cognitive function (MMSE score > 17)
- Subject is willing to be randomized to the control group or the treatment group.
- Ability to sit unsupported for 30 seconds
- Ability to walk at least 10m with maximum 1 person assist,
- Ability to follow a three-step command
- Physician approval for patient participation
- Living in the community post-stroke with ability to travel to the intervention site to participate in the outpatient program and able to perform the HEP program in the residential facility.
- Willing to carry wireless body sensors through the period of the study and to follow-up time period, post inpatient stroke, cardiac, pulmonary, or any other lower extremity physical rehabilitation

- \geq 90 days post major orthopedic surgery (i.e. hip, knee, and/or ankle joint replacement)
- \geq 6 months post CABG or cardiac valve procedure
- Able and willing to give written consent and comply with study procedures, including follow-up visits
- Willing to participate in two Transcranial Magnetic Stimulation sessions if they meet compatibility requirement.
- Cannot not be participating in any other structured outpatient or home health physical therapy program

3.2 Exclusion Criteria

- Serious cardiac conditions (hospitalization for myocardial infarction or heart surgery within 3 months, history of congestive heart failure, documented serious and unstable cardiac arrhythmias, hypertrophic cardiomyopathy, severe aortic stenosis, angina or dyspnea at rest or during activities of daily living)
- Severe arthritis or orthopedic problems that limit passive ranges of motion of lower extremity (knee flexion contracture of $> 10^\circ$, knee flexion ROM $< 90^\circ$, hip flexion contracture $> 25^\circ$, and ankle plantar flexion contracture $> 15^\circ$)
- Serious medical conditions including myocardial infarction or heart surgery within 3 months, history of congestive heart failure, documented serious and unstable cardiac arrhythmias, hypertrophic cardiomyopathy, severe aortic stenosis, angina or dyspnea at rest or during activities of daily living, Severe hypertension, severe weight bearing pain, life expectancy less than one year
- Preexisting neurological disorders such as Parkinson's disease, Amyotrophic Lateral Sclerosis (ALS), Multiple Sclerosis (MS), dementia
- History of major head trauma, Lower extremity amputation, Non-healing ulcers of a lower extremity, Renal dialysis or end stage liver disease, Legal blindness or severe visual impairment, a history of significant psychiatric illness
- Pacemakers, metal implants in the head region
- History of unexplained, recurring headaches, epilepsy/seizures/skull fractures or skull deficits
- Medications that lower seizure threshold
- History of concussion in last 6 months
- Subject is pregnant, nursing or planning a pregnancy
- Inability to travel 3 times per week for outpatient training programs
- Participating in another clinical trial that, according to the Principal Investigator, is likely to affect study outcome or confound results

4.0 TREATMENT PLAN

4.1 Treatment Sessions

Once subjects have been consented and they meet study inclusion and exclusion criteria, they will be randomly placed into either the SMA group or impairment based (IPT) group. The Physical therapy treatment sessions will follow the guidelines below:

- IPT group
 - Assessment (strength, flexibility, balance, sensation, endurance, transfers, gait). Treatment will be divided into: 15 min balance training, 15 minutes functional mobility (transfers, strength or flexibility training) and 15 min high intensity gait training

- SMA group
 - Assessment (strength, flexibility, balance, sensation, endurance, transfers, gait)
 - Treatment consists of 30minutes high intensity gait training with device, 15 minutes functional mobility with device (eg stairs, ramps, curbs, uneven surfaces, indoors, outdoors)

4.2 Duration of Therapy

The Outpatient physical therapy sessions will last for a maximum of 18 visits per subject.

